## **7.4 Method of assigning subjects to Baxter and GSK vaccine groups**

It would be desirable if vaccinees could be assigned Baxter and GSK vaccines at the same time, i.e., both vaccines arrived in each centre before regulatory approval (ethics and MHRA) is obtained. This may not occur, so procedures will be put in place to meet the following scenarios:

- A. Both vaccines arrive at each centre prior to regulatory approval:
- B. Only one vaccine arrives at each centre prior to regulatory approval:

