**9.2.3 Analysis of demographic and baseline characteristics**

Descriptive statistics (mean, standard deviation, median, minimum, and maximum) for age, together with distributions of subjects by sex and ethnic origin, previous influenza vaccination (during the past three seasons), recent influenza-like illness in the patient (since May 2009), and presence of pre-vaccination antibody to the vaccine strain will be summarized overall, for each vaccine group, and by age group.

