- Significant increase in antibody titre/area is defined as at least a fourfold increase in HI or a 50% increase in area from non-negative pre-vaccination serum ( $\geq 10$  for HI,  $\geq 4$  for SRH).

**Seroprotection:** Percentages of subjects achieving each of the following thresholds: inverse HI titre  $\geq 40$ , SRH area  $\geq 25 \text{ mm}^2$ : The number and proportion of subjects achieving each threshold at each visit will be tabulated for each vaccine/age group and each vaccine type.

All statistical analyses for HI and SRH will be performed on the logarithmically (base 10) transformed values. Titres below the limit of detection for assays will be set to 1 in 5 for HI and  $4 \text{ mm}^2$  for SRH for the purposes of analysis. Original values will be presented in all listings

The above immunogenicity criteria will be applied to sera collected 21 days after completion of vaccination, i.e., 21 days after the second vaccine dose. For pandemic vaccines, all three criteria should be met.

Should both GSK and Baxter vaccines satisfy all three CPMP criteria, we will compare the immunogenicity of the two vaccines (for each vaccine/age group and each vaccine type) in terms of:

- a. Geometric mean titres 21 days after each vaccination;
- b. Geometric mean ratio increases 21 days after each vaccination;
- c. Seroprotection rates 21 days after each vaccination;
- d. Seroconversion rates 21 days after each vaccination.

Comparisons will be made using parametric or non-parametric tests as appropriate for continuous outcomes, and Pearson's chi-square test or Fisher's exact test where appropriate for categorical outcomes. Further analyses using (generalised) linear models will explore the effect of baseline covariates on the outcomes. For populations (a) and (b), analyses using multiple imputation to allow for missing data will also be undertaken as a sensitivity analysis. No formal adjustment will be made for multiple testing but associated P-values will be interpreted cautiously.

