#### 9.2.6.1 Local and systemic symptoms

The incidences of local and systemic reactions following vaccination will be summarized by vaccine group.

The occurrence of selected indicators of reactogenicity (listed below), which by definition, can only occur up to 6 days post-vaccination, will be recorded on the Local and Systemic Reactions Diary/CRF rather than the Adverse Events CRF.

- Local reactions: Ecchymosis, erythema, induration, swelling and pain at injection site.
- Systemic reactions: Chills, malaise, myalgia, arthralgia, nausea, headache, sweating and fatigue
- Other indicators of reactogenicity: Stayed at home due to reactions, oral temperature, and use of analgesic/antipyretic medication.

If a reaction occurs more than once for a subject, the reaction will be classified according to the highest occurring severity.

All study subjects will be observed for at least 30 minutes after a vaccination for evidence of immediate reactions in general and in particular for symptoms of allergic phenomena (such as rashes, itching, or other allergic manifestations).

Each subject will be instructed to complete a diary card for 7 days following each vaccination, to describe local and systemic reactions and other selected indicators of reactogenicity. If a local and systemic reaction or fever (derived from measured oral temperatures  $\geq 38.0^{\circ}\text{C}$ ) continues beyond the 7-day period after a vaccination, it will also be recorded on the Adverse Events CRF. If the subject recovers on the last day, then this fact will be recorded on the Local and Systemic Reaction CRF.

We will summarise the occurrence of solicited local and systemic symptoms (point estimates and 95%CI) by vaccine type in terms of incidence, intensity, and relation to vaccination. We will use the two-sided Fisher's exact tests to compare groups where appropriate.

Frequencies and percentages (together with 95% CIs) of subjects experiencing each reaction will be presented for each symptom severity. Summary tables showing the occurrence of any local or systemic reaction overall and at each time point will also be presented.

The severity of local reactions, including injection-site ecchymosis, erythema, swelling, and induration, will be categorized as none, 1 to  $\leq 25$  mm, 26 to  $\leq 50$  mm and  $> 50$  mm.

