The severity of pain and systemic reactions will be categorized as none, mild (transient with no limitation in normal daily activity), moderate (some limitation in normal daily activity), and severe (unable to perform normal daily activity).

Distribution of body temperature, staying at home due to vaccine reaction and the use of analgesic/antipyretic medication occurring during 7 days after each vaccination will be tabulated. Fever will be defined as a temperature of  $\geq 38.0^{\circ}\text{C}$ , and severe fever as  $\geq 40.0^{\circ}\text{C}$ . Oral temperature will be categorized as  $< 38^{\circ}\text{C}$ ,  $38^{\circ}\text{C}$  to  $< 39^{\circ}\text{C}$ ,  $39^{\circ}\text{C}$  to  $< 40^{\circ}\text{C}$ , and  $\geq 40^{\circ}\text{C}$ .

All post-vaccination reactions (local and systemic), use of relief medication and absence from work due to any adverse events will be summarized as none *versus* any.

For the local and systemic reaction safety variables, differences among the groups after vaccination will be analyzed by using Pearson's chi-square test or Fisher's exact test where appropriate.

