#### **9.2.6.2 Adverse events**

The reporting and documentation of unsolicited events throughout the study is described in Sections 8.5 and 8.6.

The original verbatim terms used by investigators to identify adverse events in the CRFs will be mapped to preferred terms using the MedDRA dictionary. The adverse events will then be grouped by MedDRA preferred terms into frequency tables according to system organ class. All reported adverse events, as well as adverse events at least possibly related to study vaccine, will be summarized according to system organ class and preferred term within system organ class. These summaries will be presented by vaccination group. When an adverse event occurs more than once for a subject, the maximal severity and strongest relationship to the vaccine group will be counted.

Additionally, three separate summaries will be produced: (i) serious adverse events, (ii) adverse events that are possibly or probably related to vaccine, and (iii) adverse events that are unrelated to

vaccine. Data listings of all adverse events will be provided by subject. In addition, a listing of subjects withdrawn from the study because of an adverse event will be presented.

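### Reactions and adverse events are planned for summary by vaccine only, pooled over three equal age bands, although the trial allocates by age band and reports immunogenicity for each vaccine/age group.

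*Protocol*

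**What the plan says.** Protocol section 9.2.6.1 names the reporting level for solicited reactions twice: "The incidences of local and systemic reactions following vaccination will be summarized by vaccine group" and "We will summarise the occurrence of solicited local and systemic symptoms (point estimates and 95%CI) by vaccine type". Section 9.2.6.2 says of adverse events: "These summaries will be presented by vaccination group". None of these sentences mentions age.

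The tests in section 9.2.6.1 are less definite. One sentence reads "We will use the two-sided Fisher's exact tests to compare groups where appropriate"; a later one says that "differences among the groups after vaccination will be analyzed by using Pearson's chi-square test or Fisher's exact test where appropriate". Neither defines the groups. Section 9.2.6.2 states no test for adverse events.

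Other sections treat vaccine and age as separate levels and name age when it is wanted. Section 7.4 is headed "Method of assigning subjects to Baxter and GSK vaccine groups". Baseline data in section 9.2.3 "will be summarized overall, for each vaccine group, and by age group". Seroprotection in section 9.2.5.1 "will be tabulated for each vaccine/age group and each vaccine type". The exploratory models with age, vaccine type and interactions (9.2.5.3) stand under the immunogenicity objectives and are not extended to reactogenicity.

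Section 9.2.6.1 also classifies a reaction that recurs in a subject at its highest severity, without saying whether this is done within a dose or across both doses.

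**The concern.** Age is the structural factor of this design. There are 60 subjects per vaccine in each of three bands (section 6.1), separate lists per band (7.4), and an assessment by vaccine/age group of whether one dose is enough (9.2.5.2). The conclusions of section 4.0 say that antigen use must weigh immune responses together with the frequency and nature of reactions. Section 9.2.7 sends interim safety results to the Department of Health to inform vaccination strategy.

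As written, the plan would give the benefit of each vaccine by age but its reactions only as an average over bands recruited 1:1:1. If reactions or vaccine differences depend on age, a reader choosing a vaccine or a number of doses for one age band would not find the reaction rate for that band in the planned tables.

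**Working it through.** **1. What the safety wording means.** Section 7.4 uses *vaccine groups* for Baxter against GSK. Section 9.2.3 lists vaccine group and age group as separate breakdowns. Section 9.2.5.1 sets the vaccine/age level beside the vaccine-type level, so vaccine type is the level pooled over age. Read with these sections, the summaries in 9.2.6 are pooled over age.

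**2. The plan's own group size.** Section 9.2.1 recruits 60 per vaccine/age group, from at least 50 subjects and up to 17% dropout. 60 × (1 − 0.17) = 49.8, so the figure is reproduced (50/0.83 = 60.2, or 61 after rounding up). Pooled over the three bands this gives 180 per vaccine recruited, or 150 if 50 remain in each.

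**3. What pooling can hide.** The protocol states no reaction rates, so these are assumed. With equal bands, the pooled rate is the simple mean of the three.

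| Assumed rates, 18-44 / 45-64 / ≥65 | Pooled | True excess by band | Pooled excess |
|---|---|---|---|
| 70/50/30% v 30/30/30% | 50% v 30% | 40, 20, 0 | 20 |
| 60/50/40% v 30/25/20% | 50% v 25% | 30, 25, 20 | 25 |
| 60/40/20% v 20/40/60% | 40% v 40% | 40, 0, −40 | 0 |
| 50/40/30% v 50/40/30% | 40% v 40% | 0, 0, 0 | 0 |

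In row 1 the pooled excess describes the middle band and neither of the others. In row 2 it is within 5 points of every band. In row 3 opposite effects cancel. If rates do not vary with age, the pooled figure fits every band.

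**4. Whether by-age estimates are precise enough.** The 95% half-width is 1.96 × √[p(1 − p)/n], largest at p = 0.5:

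- n = 60: 1.96 × √(0.25/60) = 12.7 points
- n = 50: 1.96 × √(0.25/50) = 13.9 points
- n = 180: 7.3 points
- n = 150: 8.0 points

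With no events, the one-sided 95% upper limit is 1 − 0.05^(1/n): 4.9% at n = 60 and 1.7% at n = 180.

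**5. Whether by-age tests would have power.** For the 18-44 v ≥65 contrast of vaccine differences, with 60 per vaccine/age group, two-sided 5% and a normal approximation:

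- Row 2: contrast 0.30 − 0.20 = 0.10; SE = √[(0.24 + 0.21 + 0.24 + 0.16)/60] = 0.119; power = Φ(0.10/0.119 − 1.96) = 13%.
- Row 1: contrast 0.40 − 0 = 0.40; SE = √(4 × 0.21/60) = 0.118; power = 92%.

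Only a large age difference would be detected reliably.

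**6. What stratifying the all-ages comparison does.** The Mantel-Haenszel weight for a risk difference in each band is 60 × 60/120 = 30. Equal weights give the crude difference, so row 1 still gives 20 points. The standard error can shrink. In row 1 the crude SE is √[(0.25 + 0.21)/180] = 5.1 points; the stratified SE is √[(0.21 + 0.25 + 0.21 + 3 × 0.21)/(9 × 60)] = 4.9 points.

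**7. Doses.** Section 9.2.6.1 tabulates temperature, staying at home and analgesic use after each vaccination, and section 9.2.7 separates days 0-6 and 0-21 from days 21-27 and 21-41. The highest-severity sentence alone does not say which period it covers.

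**The case against.** The strongest reply is that table breakdowns commonly go into a statistical analysis plan, which is not shown; section 9.2.6 may be a minimum set that does not exclude by-age tables, and the reactogenicity objective in section 5.0 promises no age level. This has weight. But the section already fixes severity cut-offs, temperature bands, tests, intervals and the reporting level, and the same protocol names the vaccine/age level for immunogenicity. By-age safety tables would be an addition to what is written.

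Several stronger readings are tempting and are not supported:

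- *The pooled comparison is biased by age.* Each band is filled to 60 per vaccine under both allocation scenarios in section 7.4, so the comparison is balanced on age and is a legitimate average. Under sequential allocation, section 9.2.5.3 itself warns of temporal bias, but that is a separate matter.
- *Reactions and adverse events are tested by vaccine only.* The groups in the reaction tests are undefined. Section 6.1 uses the word for six vaccine/age groups, so that reading is open. No test of adverse events is stated.
- *The pooled rate fits no age group.* That depends on rates that the protocol does not give. The pooled rate can equal the middle band, and it fits all three if age has no effect.
- *Age differences would go unseen.* Adverse events are listed by subject and the subject number carries the age band. The by-age result is absent from the planned summaries, but it can be recovered.
- *Severity is pooled over doses throughout.* Other tables are already per vaccination; only the one rule is silent.

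**Conclusion.** The point holds as a reporting gap. Every summary of reactions and adverse events in section 9.2.6 is planned by vaccine alone, over a fixed equal mix of three age bands, while allocation is by band and immunogenicity is reported by vaccine/age group. The planned comparison remains valid as an average.

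The size of the loss is unknown because no reaction rates are stated. On assumed rates it runs from nothing, when age does not matter, to complete cancellation, when effects are opposite. By-age rates can be estimated to within 12.7 to 13.9 points at worst, which is enough to describe them. Interaction power ranges from 13% to 92% in the two cases calculated, so the by-age results should be presented as estimates with intervals and not as powered tests. The change is worth making, since the results are meant to inform national strategy and it costs little.

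**What to change.** - In sections 9.2.6.1 and 9.2.6.2, and for the safety tables in 9.2.7, present results for each vaccine/age group as well as each vaccine type. Give 95% CIs for reaction rates, and say that the by-age results are estimates and not powered tests.
- State that *groups* in both reaction-test sentences of 9.2.6.1 means the two vaccines.
- Stratify the all-ages comparison by age band, for example by Mantel-Haenszel. This matches the allocation and may tighten the standard error; it does not remove the averaging over bands, so it cannot replace the by-age columns.
- State that the highest-severity rule applies within each dose, in line with the per-vaccination tables in 9.2.6.1 and the windows in 9.2.7.

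The cost is wording and more table columns. No new subjects or data are needed, because the age band is part of the subject number (section 7.4).

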#### **9.2.6.2 Adverse events**

The reporting and documentation of unsolicited events throughout the study is described in Sections 8.5 and 8.6.

The original verbatim terms used by investigators to identify adverse events in the CRFs will be mapped to preferred terms using the MedDRA dictionary. The adverse events will then be grouped by MedDRA preferred terms into frequency tables according to system organ class. All reported adverse events, as well as adverse events at least possibly related to study vaccine, will be summarized according to system organ class and preferred term within system organ class. These summaries will be presented by vaccination group. When an adverse event occurs more than once for a subject, the maximal severity and strongest relationship to the vaccine group will be counted.

Additionally, three separate summaries will be produced: (i) serious adverse events, (ii) adverse events that are possibly or probably related to vaccine, and (iii) adverse events that are unrelated to

vaccine. Data listings of all adverse events will be provided by subject. In addition, a listing of subjects withdrawn from the study because of an adverse event will be presented.

### 9.2.7 Interim/preliminary analyses

To provide DH with information as rapidly as possible with the goal of informing DH vaccination strategy, the following interim analyses of data from this study are planned:

- Solicited/unsolicited events (local and systemic symptoms, relief medication, and absence from work due to any adverse events) during:
  - Days 0-6 (1st vaccination)
  - Days 0-21 (1st vaccination)
  - Days 21-27 (2nd vaccination)
  - Days 21-41 (2nd vaccination)
- HI and MN antibody titres on days:
  - Days 0, 7, 14, 21 (1st tranche of sera measuring antibodies before and after 1st injection)
  - Days 21, 28, 35, 42 (2nd tranche of sera measuring antibodies before and after 2nd injection).

